Overview of study. The objective of this study is to expand the reach of SHE to address women's health disparities more broadly, and to create a sustainable model for dissemination of health promotion interventions for vulnerable populations. In the first aim (Year 1), we will run a pilot study to assess feasibility of the expanded content and electronic women's health literacy intervention delivered through text-Web modality with N~10 of our original SHE participants. Feasibility outcomes include uptake of intervention components, barriers and facilitators of implementation, problems with delivery, and necessary modifications. Pilot effectiveness outcomes will include an assessment of women's health literacy, operationalized as knowledge, beliefs, and self-efficacy for screening related to cervical, breast cancer, birth control, and STIs, post-intervention.

In the second aim (Year 2-3), we will conduct an RCT with N~200 newly recruited women to test the effectiveness of the SHE-Women electronic women's health literacy intervention: the intervention arm will get SHE-Women; the control arm will get a standard of care discharge planning session and health education booklet. Assessment of effectiveness will occur on two outcomes: a) Women's health literacy, operationalized as knowledge, beliefs, and self-efficacy for screening related to cervical, breast cancer, birth control, and STIs; and an increase in COVID-19 health literacy and increase in self-efficacy for prevention immediately post-intervention and 1-year post-intervention; b) Screening/ risk reduction for cervical, breast cancer, unintended pregnancy, and STIs at 1, 2, and 3-years post-intervention (follow-up complete by Year 5).

In the third aim (Year 3-5) we will track participants and conduct key stakeholder interviews to better understand the role and impact of human interaction in electronic interventions to answer the question: how much human "touch" is needed to make an intervention effective? Outcomes will include perception and uptake of intervention components, women's health literacy, screening, and risk reduction outcomes. Table 3 describes aims, activities, outcomes, and benchmarks.

Table 3. Aims, Activities, Outcomes, and Benchmarks

Activities	Outcomes	Benchmarks for success
Aim 1. Assess feasibility and pilot effectiveness of 'SHE-Women,' an electronic women's health literacy intervention.		

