
 Finalize IRB protocol/approvals Finalize build out of expanded intervention content/ text-Web platform Re-consent N~20 women in original SHE cervix study to participate in SHE-Women via text-Web platform/ deliver SHE-Women Conduct stakeholder interviews with participants of SHE-Women pilot Conduct baseline, post-intervention assessment of women's health literacy outcomes Refine intervention content/text-Web platform for Aim 2 RCT 	
 Uptake of components Barriers and facilitators of implementation Problems with delivery Modifications needed Women's health literacy: knowledge, beliefs, self-efficacy for cervical, breast cancer, birth control, STI screening Increase in health literacy and self-efficacy for avoiding COVID-19 	
 IRB approval secured prior to study start Intervention content build out and text-Web platform ready by Y1Q3 Re-consent and deliver SHE-Women to N~50 original SHE participants from Y1Q3-Y1Q4 Key stakeholder interviews conducted between Y1Q3-Y1Q4 Refine intervention content and text-Web platform for Aim 2 RCT by Y1Q4 Manuscript #1 mixed methods pilot study to modify an electronic intervention for women leaving jail in Y1
Aim 2. Test the effectiveness of SHE-Women on women's health literacy, screening, and risk reduction practices against a standard of care discharge planning session using a randomized controlled trial.		

 Recruit N~200 women leaving jails, women in community organizations that cater to our 	
 Women's health literacy 	
 Recruit, consent, and deliver intervention and control arms to N~200 women between Y2Q1-Y3Q4

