Intervention arms and procedures. All women will be mailed a SHE-Women booklet with the intervention content. Electronic women's health literacy intervention procedures (intervention arm). e will deliver the integrated, multimedia electronic women's health literacy intervention arm of SHE-Women in text-Web format for individuals recently released from jail or have recent involvement with the criminal-legal system (2 years). Two health educators will be responsible for delivering content to participants, with an estimated contact time of ~10 hours pushed to participants over approximately a 5-day period. However, because it is a text-Web intervention, accessing content will be dependent on user engagement with the platform. We will measure uptake of the intervention components as it relates to number of minutes of engagement and length of time (total number of days) that all content was accessed. The lead health educator will describe the study and obtain consent from participants. If participants consent, they will immediately be asked to participate in a baseline survey.

For Aim 1 pilot study participants, this will occur over phone or in person in the community. For Aim 2 RCT participants – all of this will occur at the jail at the participant's time of discharge. Participants will be informed that after consent/ after they leave jail, in order to initiate the program, they should contact the health educator through phone, text message, email, or Facebook message. We estimate that we might lose 30% of women between consent and initiation of the community-based intervention, simply because they do not follow-up with us. Thus, in the Aim 1 pilot study we will over-recruit by 15 women; and in the Aim 2 RCT we will over recruit by 60 women, to make up for potential loss to attrition. To improve rates of follow-up, we will also collect multiple points of expected contact information for the participants: phone numbers, addresses for themselves or family members; usual places of hangout; and Facebook handle. That way, if participants don't reach out to us within three days of consent/release from jail, we can contact them.

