Standard of care discharge planning session (control arm). In the Aim 1 pilot study, participants will only access the intervention arm content. In the Aim 2 RCT, participants will be randomized after consent to the intervention or control arm. The women will be offered a 10-page women's health booklet that utilizes SHE-Women content, but in print form. The booklet will provide simple definitions, screening guidelines, and local health resources for age and risk appropriate cervical, breast cancer, unintended pregnancy, and STI prevention. We will collect multiple points of contact information for the participants: phone numbers, addresses for themselves or family members; usual places of hangout; and Facebook handle, for follow-up. Participants in this arm of the intervention will be contacted 5 days after receiving the standard of care intervention for post-assessment. Similar to the intervention arm, we expect to lose 30% of women to follow-up, thus we will over-recruit by about 30% for the RCT, as described above. Participants will be asked to reach out to us 5 days after or we will contact them for follow-up and to complete the post-assessment over the phone or through an electronic link to the survey.

We wish to note that although we call the control arm the "standard of care," in reality there is no standard discharge planning session in the jails we work with; women are sent out the door with their belongings. But we feel it would be grossly unethical to not provide the control arm with some health information, even if limited.

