Opportunities for human interaction – text messaging and community sessions (both arms invited). To develop a more robust measure of the impact of human interaction on intervention outcomes for Aim 3, we will invite participants from both intervention arms to participate in text messaging with a health educator if they have questions and with the opportunity for attendance at community-based women's health group sessions. To facilitate access to text messaging with a health educator, all participants will be given the health educator's study cell phone number, which she will respond to during business hours. The health educators will also hold quarterly women's health discussion sessions at two public libraries in the Kansas City neighborhoods in which >50% of our participants live.¹⁸ These are public sites where participants know how and when to access services, per our past experiences with them. All participants will be invited, regardless of randomization.

Compensation and retention. Pilot study participants will receive \$25 for completing the intervention, and \$20 for completing the stakeholder interviews. All participants of the RCT will be offered \$50 for completing the intervention. The women in the control arm will receive the same payment to be fair. Participants who complete the COVID-19 interview will receive \$10. Compensation will be placed on a debit card. We have used this method and amount of payment successfully in our previous work with these women.^{3,5,9}

Retention of participants for the annual follow-ups will be accomplished through effective methods that our research teams have developed and used successfully for the last eight years to achieve excellent follow-up

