Using quantitative data from the pilot trial of the SHE-Women text-Web intervention, we will conduct descriptive analysis and bivariate tests to explore women's health literacy (knowledge, beliefs, and self-efficacy) for screening related to cervical, breast cancer, birth control, and STIs (Aim 1). The results including effect sizes estimated for the outcome will be utilized for refinement of the intervention content and modality. To test the hypothesis that SHE-Women will be more effective than standard of care at improving outcomes (Aim 2), we will utilize mixed modeling techniques for repeated measures, separately for each outcome variable: health literacy for screening and screening/risk reduction practices. General/generalized models will evaluate the effects of the intervention by estimating overall group difference across measurements (i.e., group effect), change over time (i.e., time effect), and group difference in change (i.e., group-by-time interaction). In other words, we will evaluate whether the intervention vs. control group improves in outcomes over time. The models will account for the impacts of sociodemographic characteristics as well as other cross-cutting risk factors including tobacco use, alcohol use, criminal justice involvement, intimate partner violence, lack of continuous health care coverage or primary care contact, etc. (covariates), thereby providing unbiased estimates of the intervention effects. The models for screening/risk reduction behaviors will also consider knowledge about cervix cancer, breast cancer, birth control, or STI as an additional covariate for the respective outcome variable. Incorporating participant tracking data, descriptive analysis and bivariate tests will demonstrate the pattern and uptake of various intervention components as measured by number of participants who responded to text messages; clicks on the Website; interactive clicks on the Website, e.g. through real-time assessment of knowledge; time elapsed between text messages and Website clicks; number of outreach messages (through text, phone, or Facebook); Facebook posts/messages; chats with health educator; total minutes of contact through text, Web, chat, Facebook with each participant; and attendance at community sessions (Aim 3). General/generalized mixed modeling for repeated measures will assess the impacts of the uptake on each outcome variable of health literacy for screening and screening/risk reduction practices while controlling for the impact of sociodemographic characteristics and other risk factors. A proper covariance structure for repeated measures will be chosen for each outcome variable based on model fit (i.e., likelihood, Akaike Information Criterion, adjusted Bayesian Information Criterion). Statistical significance will be determined at 0.05 alpha level, and all analyses conducted using SAS 9.4⁵⁹

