Strategies for success, alternatives, key findings. Strategies for success include allowing for sufficient time for recruitment early in the study in case recruitment is slow, but we also draw on our successful and effective methods of recruitment, intervention delivery, and retention strategies. The integrated, mediated electronic women's health literacy intervention via text-Web delivery platform is based on carefully collected data over the last three years about use of electronic technologies among women leaving jails and extensive experience among our health communications team of developing electronic interventions. Alternative strategies in case we have problems include: having adequate time for recruitment of more participants. If we have higher than expected rates of attrition, we have adequate time, resources, and partnerships with the jails to recruit more participants. We will also leave sufficient lead time for development of the text-Web modality. We realize our methods may not allow for an ideal unbiased experimental design given convenience sampling; however, we feel that our unique access to a difficult to reach and understudied population of *prisoners* outweighs the pitfalls of utilizing convenience samples. If our hypotheses are not supported, subsequent projects will focus on discharge planning or going back to tried and true methods of face-to-face health education. Key findings from

this study will include whether a women's health literacy intervention is effective at changing intersecting behaviors among women leaving jail; whether an electronic women's health literacy intervention is feasible and effective; and how much human "touch" is ideal in an electronic intervention. Knowledge gained from this study will help develop a new paradigm for mitigating health disparities among vulnerable women.

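### Aim 2 names a standard-of-care discharge session as comparator, but the contrast described is the text-Web package added to a print booklet and optional educator contact; the null reading and power statement should say so

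*Combined protocol and SAP*

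**What the plan says.** **Named comparator.** Table 3 gives Aim 2 as: "Test the effectiveness of SHE-Women on women's health literacy, screening, and risk reduction practices against a standard of care discharge planning session". The overview of the study says "the control arm will get a standard of care discharge planning session and health education booklet". The data analysis section repeats the label: "To test the hypothesis that SHE-Women will be more effective than standard of care at improving outcomes".

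**What controls receive.** The section on intervention arms and procedures opens with "All women will be mailed a SHE-Women booklet with the intervention content". The control-arm section says "The women will be offered a 10-page women's health booklet that utilizes SHE-Women content, but in print form", and lists its contents as basic definitions, guidelines on screening and local resources. It then admits that "in reality there is no standard discharge planning session in the jails we work with". It describes no session content. The outcomes section nevertheless plans to ask controls about the conversation in a discharge session.

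**Shared contact.** The section on opportunities for human interaction offers educator texting and quarterly library sessions to both arms: "All participants will be invited, regardless of randomization". The attrition text expects about half to accept.

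**Planned reading of a null.** The section on strategies for success says "If our hypotheses are not supported, subsequent projects will focus on discharge planning", and the same sentence offers a return to face-to-face education as the alternative.

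**The concern.** The comparator in the aim and hypothesis is not the one described in the procedures. Three things depend on it.

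- **The claim.** A result reported as SHE-Women versus standard of care would be taken as the effect against ordinary release from jail. The design does not estimate that.
- **The next step.** The plan ties a null to a change of approach. If both arms improved because print and educator contact helped, the investigators could set aside a cheap format that worked.
- **The power.** Effect sizes are carried over from the original SHE study with no allowance for a control arm that itself receives health-literacy material and access to an educator.

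**Working it through.** **Step 1. Set the arms side by side.**

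| Component | Intervention | Control | Where stated |
|---|---|---|---|
| Print booklet | Yes | Yes | Intervention arms and procedures; control-arm section |
| Website content (about 10 hours), daily prompts, reminder messages and calls | Yes | No | Intervention arms and procedures; Data collection |
| Live chat through the Website | Yes | Not described | Intervention arms and procedures |
| Texting with the educator | Invited | Invited | Settings; Opportunities for human interaction |
| Community sessions | Invited | Invited | Same |
| Discharge session | Not described | Named in the overview and Table 3, no content in the control-arm section | Overview; Table 3; control-arm section |

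Randomisation separates the arms on the Website package and its prompts, calls and chat. It does not separate them on the booklet, texting or community sessions.

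**Step 2. What each result can show.** Let S be the effect of the shared components against usual release, and W the further effect of the text-Web package. The trial estimates W. The effect against usual release is S + W.

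- If W > 0 and S ≥ 0, then S + W ≥ W. A positive result is valid for W and conservative for benefit over usual release, but S + W is not estimated.
- If W is close to 0, S may be zero or positive. A null on W cannot tell these apart, and low power gives a third explanation.

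**Step 3. Reproduce the plan's power.** The Power section gives r=0.46, three measurements for literacy, N=124 and 80% power; alpha is 0.05 (Data analysis). For the group-by-time interaction with two groups, assuming sphericity:

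λ = f² × N × t / (1 − r), df1 = t − 1, df2 = (N − 2)(t − 1)

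- f=0.12, t=3, N=124: λ = 0.0144 × 124 × 3 / 0.54 = 9.92, df 2 and 244, power 80.7%. This matches the stated 80%.
- f=0.13, t=3, N=124: λ = 0.0169 × 124 × 3 / 0.54 = 11.64, power 86.9%. This does not match.

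The section says it assumes 0.12 and then prints 0.13. That is a separate matter, so both are carried forward.

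**Step 4. Sensitivity to a smaller contrast.** The documents do not say how far the enhanced control would shrink f. A 25% cut is an illustrative assumption: 0.12 × 0.75 = 0.09 and 0.13 × 0.75 = 0.0975. N=170 is Table 4's 1-year figure, the last literacy time point; N=200 is its post-intervention figure.

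| t=3, r=0.46 | N=124 | N=170 | N=200 |
|---|---|---|---|
| f=0.12, no cut | 81% | 92% | 96% |
| f=0.09: λ | 5.58 | 7.65 | 9.00 |
| f=0.09: power | 55% | 69% | 77% |
| f=0.13, no cut | 87% | 96% | 98% |
| f=0.0975: λ | 6.55 | 8.98 | 10.56 |
| f=0.0975: power | 62% | 77% | 83% |

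With a 50% cut from 0.12 (f=0.06), power is 27%, 36% and 41% at the same three sizes. At the plan's own worst case, 200 × 0.60 = 120, the uncut f=0.12 gives 79.3%, so there is no margin for any cut. For the four-measurement screening outcomes, f=0.09 gives 61% at N=124 and 71% at N=150, Table 4's 3-year figure.

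**The case against.** **The controls' extras are disclosed and justified.** The overview mentions the booklet, the control-arm section gives an ethical reason for it, and inviting both arms to educator contact serves Aim 3. This stands. It supports keeping the arms, but does not make the control standard of care.

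**Modality is already a stated goal.** The significance section makes testing the modality its second goal, and the list of key findings asks separately whether an electronic intervention works. One of the two fallbacks after a null keeps health education and drops only the electronic mode. A reader might infer that the plan would treat a null as failure of the literacy programme; the full sentence does not say that. What remains is that neither fallback follows from a null without looking at change in both arms.

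**The arms are not equivalent in content.** A reader might infer that controls get the whole programme in print. The mailing sentence invites that reading, but the control-arm section describes a 10-page summary, against roughly 10 hours of electronic material with prompts, calls and chat. Equivalence is not shown.

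**The effect sizes may not be waitlist effects.** The progress report names a waitlist control only for the post-intervention literacy result and does not say what that group received. The smallest effect, f=0.12, is 1-year condom use, and its comparator is not stated. So it cannot be asserted that the power rests on contrasts with an untreated group, only that no allowance is made for this control.

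**The analysis already covers part of this.** The models include time and group-by-time terms, and educator contact is tracked. Reporting change and contact by arm therefore needs little beyond what is planned.

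**Conclusion.** The comparator is misnamed and the documents contradict each other on what controls receive. As described, Aim 2 estimates the added effect of the text-Web package over a booklet plus optional educator contact.

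A reader might conclude that neither a positive nor a null result would be informative. That goes too far. A positive result is a sound randomised contrast against the control actually given. It is conservative against usual release provided the booklet and contact do no harm. It does not give the size of that wider effect. The weakness lies with a null, which the plan links to a change of approach without asking whether both arms gained.

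The size of the power problem is conditional. With an assumed 25% shrinkage, literacy power is about 55% to 77% from f=0.12 and 62% to 83% from f=0.13, over N=124 to 200. The lower ends apply at the smallest sample; Table 4 expects more women at the literacy time points. The documents neither support nor exclude a particular shrinkage, so these figures show sensitivity and are not a forecast.

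**What to change.** Keep the arms and the data collection, and change the following.

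1. Reconcile the overview, Table 3, the intervention and control-arm sections and the outcomes section on what controls receive: whether any session takes place, and whether the mailed booklet and the 10-page booklet are the same.
2. Restate Aim 2 and its hypothesis as text-Web package plus booklet versus booklet, both with optional educator texting and community sessions. If reconciliation shows that a session is delivered, add it to the control's description.
3. Limit the conclusion to that added value, with no estimate claimed against usual release.
4. Report within-arm change and educator contact for each arm beside the between-arm result.
5. Amend the strategies section so that a null is read with change in both arms, and with the precision of the contrast, before the next approach is chosen.
6. In the Power section, state the comparator behind each effect size (waitlist for the post-intervention literacy result, currently unstated for the 1-year effects) and add a sensitivity for a smaller contrast, such as the table above.

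The cost is wording, a narrower claim and a less favourable power statement.

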Participants who successfully initiate the intervention, over a 5-day period will be sent texts to their mobile phone or messaged through email or Facebook (participant preference) with a link to content on a SHE-Women Website. Content will correspond to Table 2, with tabs for Knowledge, Beliefs, Self-efficacy, Confidence navigating systems, and Wrap-up/review. Content will be delivered through a mix of short videos of the health educators and standardized patient actors discussing content (available in video and audio only format), interactive quizzes, and plain text. Although participants will be able to access content in all five areas, they will receive a daily text message for each area. For example, on Day 1, they will receive a text message to engage in Knowledge content; Day 2, a message to engage in Beliefs content; Day 3, a message to engage in

Self-Efficacy content; Day 4, a message to engage in Confidence navigating health systems content; and on Day 5, a message to complete Wrap-Up content and be invited to complete post-intervention assessments.

A second health educator will monitor whether participants access content after receiving the text messages. If participants have not accessed content within 24 hours of receiving a text message prompt, they will be sent a second text message invitation. If participants still haven't responded, they will receive a phone call from the lead health educator, or a video message through Facebook, that is directly geared toward the participant, re-inviting them to access content for that day.

The SHE-Women Website will also have a tab available to live-chat with a health educator 5 days a week for 8 hours a day. Participants will be able to send messages to the health educator through the SHE-Women Website, if they are not able to live chat. This feature will be available in addition to standard text-message access to a health educator during business hours. We will add weekend or evening hours if necessary.

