Although the text-Web intervention will be designed to be accessed over a continuous 5-day period; participants will be given a three-week window to access all intervention content, to allow for self-directed completion of the text-Web intervention. As soon as participants access all intervention content, the second health educator will be triggered to complete a post-intervention assessment. The post-assessment will be offered to participants over the phone or through an electronic link to the survey.

We will not provide participants equipment or electronic devices. The goal of this project is to assess whether a text-Web intervention is feasible and effective in real life circumstances, thus, with the participants' own devices. We will not pay for any data usage charges to participants. However, because we are compensating participants for study participation, they can use some of the money from study compensation to cover any data usage costs incurred. There are no limitations on what devices can be used. Though participants will have to either receive initial text messages either through a mobile phone or through a private Facebook message. A third option could be through an email address. Participants will then need to be able to access Web content, but they can do that at any place of their choosing: a mobile phone, a home computer, a public library computer, or at some other place.

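### Intervention-arm women who never initiate have no stated route to the immediate post-intervention literacy assessment, whereas controls are contacted without any engagement step

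*Combined protocol and SAP*

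**What the plan says.** All of this is in the protocol, mainly under Intervention arms and procedures.

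- **Intervention arm, first route.** "Participants who successfully initiate the intervention, over a 5-day period will be sent texts to their mobile phone or messaged through email or Facebook". On Day 5 of that series the woman receives "a message to complete Wrap-Up content and be invited to complete post-intervention assessments".
- **Intervention arm, second route.** "As soon as participants access all intervention content, the second health educator will be triggered to complete a post-intervention assessment". For this, "participants will be given a three-week window to access all intervention content".
- **Before initiation.** After consent and release the woman has to contact the health educator to start. "We estimate that we might lose 30% of women between consent and initiation of the community-based intervention". If women do not "reach out to us within three days of consent/release from jail, we can contact them". That outreach is not linked to an assessment.
- **Control arm** (Standard of care discharge planning session). "Participants in this arm of the intervention will be contacted 5 days after receiving the standard of care intervention for post-assessment". Staff make the contact if the woman does not. She need not have read or used the booklet. A 30% loss is expected here too.
- **Randomisation.** In the RCT, "participants will be randomized after consent to the intervention or control arm".
- **Expected numbers** (Table 4, RCT column). 260 at consent and baseline, 220 at initiation, 200 at post-intervention, not split by arm.
- **Missing data** (Power; Data analysis). Multiple imputation within an intent-to-treat analysis. Auxiliary variables are allowed but not named.

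**The concern.** Both intervention-arm routes open only after the woman has done something following randomisation: started the programme, or finished its content. In the control arm the contact follows from receipt of the material. A partial user still gets the Day-5 invitation, so the gap concerns only women who never initiate.

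Immediate literacy is a stated Aim 2 outcome and one of the three measurements in the literacy model (t=3 under Power). If its ascertainment follows engagement in one arm and reachability in the other, the women observed in the two arms are no longer comparable by randomisation at that visit. Imputation cannot supply what is absent. No never-initiator would have an observed immediate score, so her value would be borrowed from women who did engage, from her baseline, and from her 1-year score if she gives one.

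**Working it through.** **1. Is any other route stated?**

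- Table 3 lists a post-intervention assessment among the Aim 2 activities but does not say how a non-initiator is approached.
- Data collection gives the survey mode (web link, phone or in person) but no trigger.
- The three-day outreach concerns starting the programme and names no assessment.
- The recruitment and attrition text replaces early losses by over-recruiting.

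None of these sets an assessment for a never-initiator.

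**2. Does randomisation come before initiation?** Randomisation is placed after consent. Initiation is described only for the intervention arm, and the control section likens its 30% loss to that of the intervention arm, which puts the loss inside an arm. Data analysis guards against re-randomising women at recruitment. The order is therefore likely, but it is inferred.

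**3. How many women?** From Table 4:

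- Loss before initiation: 260 − 220 = 40, and 40/260 = 15.4%.
- Loss between initiation and post-intervention: 220 − 200 = 20.
- Total: 40 + 20 = 60, and 60/200 = 30%.

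The text's 30% is tied to over-recruiting 60 women, so it may be the total early loss. Applied to initiation alone it would leave 260 × 0.70 = 182, not the 220 in Table 4. With an assumed 130 per arm, 130 × 0.154 = 20 intervention-arm women lack a stated route.

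**4. Illustration of size.** Let p be the non-initiation share and k the share of the engaged women's effect that reaches never-initiators (assumed). Let g be the ratio of the 1-year to the immediate effect, and b the weight of the 1-year score in the imputation given baseline.

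- True effect, in units of the engaged effect: (1 − p) + pk.
- Imputed effect for a never-initiator: 1 − b(1 − k)g.
- Relative overstatement: p(1 − k)(1 − bg) / [(1 − p) + pk].

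Inputs: p = 0.154 from Table 4; g = 0.16/0.13 = 1.23 from the effect sizes under Power; b = r/(1 + r) under an assumed common correlation r. The average r = 0.46 under Power gives b = 0.46/1.46 = 0.315. Without a 1-year score, b = 0.

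| Assumption | No 1-year scores | All give 1-year scores (r = 0.46) |
|---|---|---|
| k = 0 | 0.154/0.846 = 18.2% | 18.2% × (1 − 0.315 × 1.23) = 11.1% |
| k = 0.5 | 0.077/0.923 = 8.3% | 8.3% × 0.612 = 5.1% |
| k = 1 | 0 | 0 |

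Over the stated baseline-to-1-year range of r, the 11.1% becomes 13.7% (r = 0.25) or 9.7% (r = 0.61).

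**5. In the three-measurement model.** If 1-year scores are observed and the two post-baseline effects are averaged, the k = 0 figure falls to 11.1% × 0.13/(0.13 + 0.16) = 5.0%.

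These are relative errors in a real effect. With no true effect, this mechanism adds nothing.

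**The case against.** The strongest reply is that never-initiators are mostly women who cannot be reached. The protocol describes them as lost because they do not follow up with the team, and it already has staff try them after three days. Many would miss an assessment call too, and the same 30% loss is expected in controls. This stands in part: it limits both the bias and the number of women a fix would recover. It does not remove the point, because equal numbers missing do not make the missing women alike.

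It can also be said that the message series and trigger are only the workflow for platform users, and that Table 3 and Data collection are unconditional. Staff could indeed assess a never-initiator, but nothing written asks them to. If randomisation in fact waited for first contact, the gap would close, so the order needs stating. Control contact also hangs on receipt of material that is mailed or offered, but that is a delivery event and not engagement by the woman.

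Uptake data could enter the imputation as auxiliary variables. That would remove the overstatement if benefit rises linearly from zero with uptake, but would not help if benefit is flat among initiators. The plan does not say whether uptake is used.

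Three stronger readings are tempting and are not supported:

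- **Overstatement of 43%, or 26% with 1-year scores.** This follows from 30% non-initiation (0.30/0.70 = 42.9%; × 0.612 = 26.2%). The 30% may be total early loss, and Table 4 gives 15.4%. Placing all 40 losses in one arm of 130 (30.8%) would give similar figures, but Table 4 is not split by arm.
- **Bias certainly favouring the intervention.** The illustration assumes imputation within arm. The plan does not specify this, and leaving arm out would pull imputed scores toward the pooled mean.
- **A known rise in false positives.** Selection on prognosis could create a spurious difference, but the documents give nothing from which to size it.

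**Conclusion.** The point holds as a gap in the written procedure, limited to never-initiators and to the immediate literacy assessment. As written, ascertainment at that visit depends on post-randomisation engagement in one arm only, and the planned imputation has no observed immediate score from the women concerned. This rests on randomisation preceding initiation.

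About 15% of women may be affected, if the Table 4 loss is spread evenly over the arms. The direction and size of the bias are not derivable. The 18% and 11% figures rest on assumed zero gain and on imputation as if engaged; they shrink with partial benefit and in the three-measurement model. The 1-year literacy outcome and the 1-, 2- and 3-year screening outcomes carry no such trigger and are not affected in this way. It should be fixed because the remedy is cheap, not because a bias has been demonstrated.

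**What to change.** Under Intervention arms and procedures, attempt the immediate post-assessment for every randomised woman in both arms, whether or not she has initiated or opened content. Use the contact details and the phone or link survey already planned.

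- Women who complete the content keep the current trigger.
- The others are approached by a fixed deadline counted from randomisation or release, for example three weeks. The existing access window cannot serve, because it has no start date for a woman who never initiates.
- State when randomisation occurs, and analyse all randomised women.
- Add a sensitivity analysis that imputes never-initiators' missing immediate scores from the control arm.
- Report assessment completion and timing by arm and by initiation status.

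The cost is protocol and analysis wording plus modest outreach: about 20 more women approached under the assumptions above, not all of them reachable. Some intervention-arm assessments will fall later than the controls' 5 days, which is why timing should be reported.
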